4.2 Endpoints

Primary Endpoints:

- The percentages of subjects with, and the frequencies and intensities of solicited local adverse events (AEs) reported on the day of vaccination and the 7 subsequent days (Days 1-8).
- The percentages of subjects with, and the frequencies, intensities and relationship to vaccination, of solicited systemic AEs reported on the day of vaccination and the 7 subsequent days (Days 1-8).
- The duration (in days) of solicited local AE, of solicited systemic AE and of the individual solicited AEs.
- The percentages of subjects with and frequencies and intensities of any unsolicited and related unsolicited AEs reported on the day of vaccination and the 28 subsequent days (Days 1-29).
- The percentages of subjects with and frequencies and relationship to vaccination, of any serious adverse events (SAEs) and any MAAEs up to 12 months post last dose.
- The percentages of subjects with and frequencies and relationship to vaccination of any adverse events of special interest (AESIs) up to 12 months post vaccination.

Secondary Endpoints:

For safety

- The percentages of subjects with and frequencies of SAEs and MAAEs related to study vaccination from 12 months post last dose up to 24 months post last dose (trial end).
- The percentages of subjects with and frequencies and relationship to vaccination of any AESIs from 12 months post last dose up to 24 months post last dose (trial end).

For the characterization of the humoral immune response

- Percentages of subjects with rabies-specific serum VNTs ≥ 0.5 IU/ml by trial group on Days 1 (pre-vaccination), 15, 43, and 12, 18* and 24* months post last dose.
- Serum geometric mean titers (GMTs) of VNTs by trial group on Days 1, 8, 15, 29, 36, 43, 57, 91, and 6 and 12, 18* and 24* months post-last dose.

* Will be performed only in subjects with detectable RABV-G-specific IgG at 6 months after the last vaccination or Day 91 if the Month 6 blood sample is not available.

Exploratory Endpoints:

For the evaluation of the innate immune response:

- Serum cytokine concentrations* including but not limited to CXCL10, CCL3, IL-6, TNF- α and IFN- γ , at pre-vaccination and 4 hours post-vaccination on Day 1, and Days 2 or 3** and 8 after each vaccination.
- Transcriptome profiling* on the day of vaccination at pre-vaccination, and Days 2 or 3** and 8 after each vaccination.

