The occurrence of AEs (serious and non-serious) will be assessed by non-directive questioning of the subject at each visit. AEs volunteered by the subject during or between visits as subject diary card entries or detected through observation, physical examination, laboratory test, or other assessments during the entire trial, will be documented. Subjects will be instructed that they must immediately report any AEs with serious symptoms, subjective complaints or objective changes in their well-being to the investigator or the clinic personnel, regardless of the perceived relationship between the event and the test vaccine.

SAEs, MAAEs and AEs leading to trial or vaccine withdrawal will be collected up to 12 months after the last dose administration. After Visit 15 (Month 12), only SAEs and MAAEs that according to the investigator are considered to be related to study vaccination will be collected.

Intercurrent medical conditions and AESIs will be collected throughout the trial.

Clinical laboratory testing for safety evaluations are provided in Appendix 6. Definitions and procedures for recording, evaluating, follow-up and reporting of AEs are provided in Appendix 11.

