9.4.14 Visit 12 (Day 57)

The following procedures will be performed during Visit 12:

- Physical examination (including weight and general condition).
- Diary review and collection for unsolicited AEs occurring up to Day 57 (Dose 2 CV7202; Dose 3 Rabipur®).
- Safety assessments (unsolicited AEs, SAEs, intercurrent medical conditions, AEs leading to trial or vaccine withdrawal, AESIs and MAAEs, concomitant medications and vaccinations).
- Blood draw for:
 - Safety laboratory (~9 ml).
 - Immunogenicity – VNTs (~18 ml), IgM/IgG/IgA (~6 ml), immune receptor sequencing (~5 ml).

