9.4.16.2 Optional Visit 14A

Visit 14A may be conducted only in case Visit 14 was conducted as a phone call, and when restrictive measures related to COVID-19 no longer prevent site visits, and the window of Visit 14 has expired. Visit 14A allows the trial procedures, including the blood draws for safety and immunogenicity testing, to occur during a widened visit window starting the day after the expiry of the original visit window and lasting up to 3 months after the original projected visit date (+15-90 days). In that case, all procedures as described in Section 9.4.16.1 for Visit 14, including blood sampling for safety and immunogenicity assessments, should be performed at Visit 14A.

Also, in case Visit 14 was conducted on site but not all procedures could be performed, Visit 14A should be scheduled on site within the protocol-allowed time interval for Visit 14A (+15-90 days).

9.4.17 Visit 15 (Month 12: Day 365 [1-dose groups]/ Day 393 [2-dose groups and Group 1 (Rabipur[®])]

9.4.17.1 Visit 15

The following activities will be performed during Visit 15:

- Physical examination (including weight, and general condition) and vital signs check (body temperature, pulse, blood pressure).
- Safety assessments (SAEs, intercurrent medical conditions, AEs leading to trial or vaccine withdrawal, AESIs and MAAEs, concomitant medications and vaccinations).
- Blood draw for:
 - Safety laboratory (~9 ml) (section 9.5.1).

- Immunogenicity – VNTs (~18 ml), IgM/IgG/IgA (~6 ml), PBMCs* for CMI (~40 ml), immune receptor sequencing (5 ml) (section 9.5.3).
* PBMCs will be taken for a subset of the first 5 subjects in Group 2 and all subjects in Groups 1, 3 and 4.

In case Visit 15 cannot take place on site due to the public health emergency related to COVID-19, safety information should be collected via a phone call within the protocol-allowed time interval for Visit 15 (± 30 days).

9.4.17.2 *Optional Visit 15A*

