Visit 15A may be conducted only in case Visit 15 was conducted as a phone call, and when restrictive measures related to COVID-19 no longer prevent site visits, and the window of Visit 15 has expired. Visit 15A allows the trial procedures, including the blood draws for safety and immunogenicity testing, to occur during a widened visit window starting the day after the expiry of the original visit window and lasting up to 3 months after the original projected visit date (+31-90 days). In that case, all procedures as described in Section 9.4.17.1 for Visit 15, including and blood sampling for safety and immunogenicity assessments, should be performed at Visit 15A.

Also, in case Visit 15 was conducted on site but not all procedures could be performed, Visit 15A should be scheduled on site within the protocol-allowed time interval for Visit 15A (+31-90 days).

If no blood sampling could be performed at Visit 15 and 15A, the end-of-trial blood sample for safety assessment may be performed at Visit 17 (Month 24: Day 729).

9.4.18 *Visit 16 (Month 18: Day 547)*

9.4.18.1 *Visit 16*

The following activities will be performed during Visit 16:

- Safety assessments (SAEs related to study vaccination, MAAEs related to study vaccination, intercurrent medical conditions, AESIs and concomitant medications and vaccinations).
- Blood draw for immunogenicity (only in subjects with detectable RABV-G-specific IgG at 6 months after the last vaccination or Day 91 if the Month 6 blood sample is not available) – VNTs (~18 ml), IgG (~6 ml) (section 9.5.3).

In case Visit 16 cannot take place on site due to the public health emergency related to COVID-19, safety information should be collected via a phone call within the protocol-allowed time interval for Visit 16 (± 30 days).

9.4.18.2 *Optional Visit 16A*

Visit 16A may be conducted only in case Visit 16 was conducted as a phone call, and when restrictive measures related to COVID-19 no longer prevent site visits, and the window of Visit 16 has expired. Visit 16A allows the trial procedures, including the blood draws for immunogenicity testing, to occur during a widened visit window starting the day after the expiry of the original visit window and lasting up to 3 months after the original projected visit date (+31-90 days). In that case, all procedures as described in

Section 9.4.16.1 for Visit 16, including blood sampling for immunogenicity assessment, should be performed at Visit 16A.

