11.2.2 Unsolicited Adverse Events

Serious AEs, intercurrent medical conditions, AEs leading to trial or vaccine withdrawal, AEs of special interest (AESIs) and MAAEs will be collected by the investigator in the eCRF throughout the trial.

AEs with a suspected potential immune-mediated disease etiology will be considered AESIs. The investigator will assess if an AE is an AESI. A list of AESIs is provided in Appendix 10 of the protocol.

AEs that are reported as related to the test vaccine will be considered trial vaccine-related; missing classifications concerning trial vaccine relationship will also be considered trial vaccine-related.

Every unsolicited AE will be assigned to a vaccination dose (number) by consideration of the period of 28 days after vaccination administration. Unsolicited AEs can be assigned to either day 1 to 28 (dose 1 for any vaccination group), or day 29 to 57 (dose 2 for 2-dose regimens or dose 3 for the Rabipur group). For the Rabipur group, vaccination dose 2 is administered 8 days after vaccination dose 1, therefore no assignment of unsolicited AEs to vaccination dose 2 is done for the Rabipur group.

All AE summaries will be restricted to those AEs that occurred after the first administration of the trial product. Any other AE (ie, AE starting after trial entry and before the first vaccination) will be reflected only in the data listings. If it cannot be determined whether the AE occurred after the first administration of the trial product due to a partial onset date, then it will be counted as such. Verbatim terms in the eCRFs will be mapped to preferred terms (PTs) and system organ classes (SOCs) using the Medical Dictionary for Regulatory Activities (version 21.0 or higher).

The occurrence of unsolicited AEs reported on the day of vaccination and the 28 subsequent days will be presented. In addition selected AE summary tables will be repeated for unsolicited AEs occurring at any time after the first administration of the trial product.

Each AE summary will be displayed by vaccination group and dose regimen. Summaries by vaccination dose (number) will also be provided for all AEs. Summaries that are displayed by SOC and PT will be ordered by descending order of incidence of SOC and PT within each system organ class. Summaries will display number and percentage of subjects with at least 1 event and the number of events by vaccination group.

Summaries of the following types will be presented:

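### All-cause SAE and MAAE collection is tied to Visit 15, which may fall up to 30 days before the 12-month primary window closes, and the documents conflict on when collection ends

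*Protocol*

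**What the plan says.** Protocol 4.2 makes the percentages, frequencies and relationship to vaccination of "any serious adverse events (SAEs) and any MAAEs up to 12 months post last dose" a primary endpoint. SAP 11.1 carries this over.

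Protocol 9.2 gives two end points in adjacent sentences. The first collects SAEs and MAAEs for 12 months from the last dose. The second switches at a visit: "After Visit 15 (Month 12), only SAEs and MAAEs that according to the investigator are considered to be related to study vaccination" are collected afterwards. The synopsis and section 10.3.5 repeat the switch.

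Table 2.1 and section 9.4.17.1 give Visit 15 a window of ± 30 days. Its safety list covers all SAEs and MAAEs. The Visit 16 list (9.4.18.1) begins "Safety assessments (SAEs related to study vaccination, MAAEs related to study vaccination, intercurrent medical conditions", and Visit 17 (9.4.19.1) has the same restriction.

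Two other passages set longer periods. The observation-period paragraph of Appendix 11 runs AE collection from consent to the end of the trial. SAP 11.2.2 says that SAEs, intercurrent conditions, AEs leading to withdrawal, "AEs of special interest (AESIs) and MAAEs will be collected by the investigator in the eCRF throughout the trial".

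A smaller matter of the same kind is the last unsolicited-AE diary. Section 9.4.14 (Visit 12, Day 57 ± 2) specifies "Diary review and collection for unsolicited AEs occurring up to Day 57" after the last CV7202 or Rabipur dose.

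**The concern.** The endpoint window is set by time since the last dose, while the switch to related-only collection is set by a visit date. When Visit 15 is early, the switch comes before the window closes. An unrelated SAE or MAAE starting in between belongs to a primary endpoint, but no later visit list asks for it under those headings.

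Safety is the primary objective and the dose-regimen groups are small (8 or 10 planned subjects), so single events matter. Coverage would also differ between subjects for scheduling reasons alone.

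**Working it through.** **Inputs.** Month 12 is Day 365 for one-dose subjects and Day 393 for two-dose subjects and Group 1 (Table 2.1 notes). The last dose is nominally on Day 1 or Day 29 (Table 8.1). Visit windows are ± 30 days for Visit 15 and ± 2 days for Visit 12 (Table 2.1). The plan has 52 subjects, with 10, 8 and 8 in Groups 1, 3a and 4a.

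**1. The plan's own day numbers.** 1 + 364 = 365 and 29 + 364 = 393, so 12 months means 364 days after the last dose. For the diary, 29 + 28 = 57. All three reproduce.

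**2. Largest shortfall at Month 12.**
- One-dose: 365 − 30 = Day 335, and 335 − 1 = 334 days after the dose.
- Groups 1, 3a and 4a: 393 − 30 = Day 363, and 363 − 29 = 334 days.
- Shortfall: 364 − 334 = 30 days; 30/364 = 8.2%.
- Latest Visit 15: 364 + 30 = 394 days, so all-cause coverage up to Visit 15 can range from 334 to 394 days.

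**3. Average shortfall (assumption: Visit 15 equally likely on each day of its window).** (1 + 2 + … + 30)/61 = 465/61 = 7.6 days; 7.6/364 = 2.1%.

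**4. Events at stake (assumption: r unrelated SAEs or MAAEs per subject-year; the documents give no rate).**
- Every subject seen 30 days early: 52 × r × 30/365, which is 0.2 events at r = 0.05 and 4.3 at r = 1.0.
- Visits spread evenly: 52 × r × 7.62/365, which is 0.05 and 1.1.
- These are upper figures for each scenario, because they assume that no other route catches the event.

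**5. Stated end of all-cause SAE/MAAE collection.**

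| Place | End point |
|---|---|
| Protocol 9.2, one sentence | 12 months after last dose |
| Protocol 9.2, next sentence; synopsis; 10.3.5 | Visit 15 |
| Visit lists 9.4.17 to 9.4.19 | all events at Visit 15, related only at Visits 16 and 17 |
| Appendix 11, observation period | end of trial (all AEs) |
| SAP 11.2.2 | throughout the trial |

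**6. Analysis.** SAP Appendix C plans unsolicited-AE tables for the 28-day window (14.3.1.2) and for the whole trial (14.3.1.3). None is cut at 12 months. The whole-trial tables would pool all-cause periods of unequal length with a related-only period.

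**7. Diary.** Earliest Visit 12 is 57 − 2 = Day 55, which is 26 days after a Day 29 dose and 2 days short of 28. As a share of the 29 diary days, 2/29 = 6.9%. This concerns 10 + 8 + 8 = 26 planned subjects.

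**The case against.** The strongest reply is that the documents do not settle on a loss. The sentence before the switch in 9.2 still promises collection to 12 months. Section 9.2 also requires open questioning about serious and non-serious AEs at every visit, and immediate reporting of serious symptoms whatever their supposed cause. Visit 16 asks about intercurrent medical conditions and concomitant medication, and SAP listing 16.2.7.1.1 carries the MAAE and intercurrent flags on the same AE record. An unrelated illness in the gap therefore has a route to the database. If an early Visit 15 was a phone call followed by Visit 15A, the full Visit 15 list is repeated 31 to 90 days after the planned date.

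This stands as far as it goes: events may be caught. It does not say which rule governs, and the Visit 16 and 17 lists follow the narrowest one. SAP section 11 refers back to Protocol 9.2 for collection, so it returns the reader to the same conflict.

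A late Visit 15 lengthens all-cause collection. That is true, but days after 12 months cannot replace missing days within a 12-month endpoint.

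On the diary, the reply largely succeeds. Under SAP 11.2.1, an individually named diary event is also entered on the AE pages and analysed there, and AE questioning continues at Visit 13. SAP 6.4 reports 53 subjects already observed to Day 57.

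**Conclusion.** The point holds as a conflict between rules that may shorten a primary window. The exposure is at most 30 of 364 days (8.2%) per subject, and about 7.6 days on average if visits are spread evenly. It arises only in subjects seen early and only for SAEs and MAAEs judged unrelated. Related events and all AESIs continue to be collected.

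The diary is a minor note: up to 2 days in about 26 planned subjects, a possible small gap for non-serious events without medical attention.

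Three stronger readings are tempting but unsupported:
- **That events are definitely not collected.** Section 9.2 itself, Appendix 11 and SAP 11.2.2 all contain longer rules.
- **That up to 4 diary days are lost after a Day 31 dose.** This needs the Visit 12 window to be counted from Day 1, which the documents do not state.
- **That the share of events judged related is inflated.** The endpoints are percentages of subjects and frequencies, not that ratio, and no actual loss is established.

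**What to change.** 1. In Protocol 9.2, the synopsis and 10.3.5, define all-cause SAE and MAAE collection by onset date: up to Day 365 for one-dose subjects and Day 393 for Groups 1, 3a and 4a.
2. In 9.4.18.1, have Visit 16 ask for all SAEs and MAAEs in any gap between an early Visit 15 and that date.
3. Align 9.4.17 to 9.4.19, Appendix 11 and SAP 11.2.2 with the same rule.
4. In the SAP, add SAE and MAAE tables cut at 12 months after the last dose.
5. If follow-up is already complete, report each subject's actual all-cause coverage in days, from the visit dates that SAP 11.3 already lists, and tabulate with the 12-month cut.

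The diary needs no more than a note in the report for subjects whose Visit 12 came before day 28 after the last dose.

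The cost is wording, one extra question at Visit 16 and a few tables. No added visit or blood draw is needed.

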9.3 Immunogenicity Assessments

The following immunogenicity assessments will be made:

Rabies-specific serum VNTs will be measured using the WHO-recommended rapid fluorescent foci inhibition test (RFFIT) before and after vaccination on Days 1, 8, 15, 29, 36, 43, 57, 91, and 6, 12, 18 and 24 months post-last dose.

The percentages of vaccine recipients with VNTs ≥ 0.5 IU/ml (WHO-recommended threshold correlating with protective immune responses) will be determined for each trial group. An antibody titer of 0.5 IU/ml serum is viewed as a surrogate of protection and defines seroconversion [26]. GMTs by treatment group will be calculated based on the VNTs on Days 1, 8, 15, 29, 36, 43, 57, 91, and 6, 12, 18 and 24 months post-last dose. VNTs assessments will be performed in a GCP-compliant laboratory.

Note that VNTs assessments at 18 and 24 months after the last vaccination will only be performed in subjects with detectable RABV-G-specific IgG at 6 months after the last vaccination or Day 91 if the Month 6 blood sample is not available.

RABV-G-specific IgM, IgG and IgA serum antibody levels will be measured by enzyme-linked immunosorbent assay (ELISA) on Days 1, 8, 15, 29, 36, 43, 57, 91, and 6 and 12 months post-last dose. In addition, RABV-G-specific IgG serum antibody levels will be measured at 18 and 24 months after the last vaccination in subjects with detectable RABV-G-specific IgG at 6 months after the last vaccination or Day 91 if the Month 6 blood sample is not available.

Additional immune-related effects will be assessed by exploratory analyses in peripheral blood samples, including measurements of serum cytokines, chemokines, and other soluble factors. These analytes include but are not limited to chemokine (C-X-C motif) ligand (CXCL)10, chemokine (CC motif) ligand (CCL)3, interleukin-6 (IL-6), tumor necrosis factor- α (TNF- α) and interferon- γ (IFN- γ) on Days 1 (at pre-vaccination and 4 hours post-vaccination), 2 or 3 and 8 after each vaccination. Gene expression changes in peripheral blood will be determined by transcriptome profiling on Days 1 (at pre-vaccination), 2 or 3 and 8 after each vaccination. Cytokine assessments and transcriptome profiling will only be performed in the first 5 subjects in Group 2 (on Day 3) and all subjects in Groups 3 and 4 (on Day 2). Note that Day 3 post-vaccination was planned in the original protocol and only applies to subjects in Group 2 who were already enrolled and vaccinated before this protocol amendment was issued. Day 2 post-vaccination applies to all other subjects.

RABV-G-specific CD4 $^{+}$ and CD8 $^{+}$ T-cell responses will be determined by intracellular cytokine staining after 6-hour incubation of PBMCs in the presence of overlapping peptides covering the open reading frame of RABV-G on Days 1, 8, and 36. The groups will be tested in their entirety at Day 91 and 6 and 12 months post-last dose if there is a significant increase in T-cell response at Day 8 or 36 compared to baseline.

RABV-G-specific circulating B cells will be determined in PBMC samples by enzyme-linked immunospot (ELISpot) assay after short-term cell culture on Days 1, 8 and 36. The groups will be tested in their entirety at Day 91 and 6 and 12 months post-last dose if there is a significant increase in B-cell response at Day 8 or 36 compared to

baseline. Lymphocyte phenotyping will be performed by conventional flow cytometry or cytometry by time of flight (CyTOF).

The humoral immune response against RABV-G will be further characterized by immune receptor sequencing of peripheral B cells, on Days 1, 8, 29, 36, 57, 91, and 6 and 12 months post-last dose in a subset of subjects; and measurement of antibody affinity and avidity, measurement of VNTs against additional heterologous lyssavirus strains and identification of epitopes recognized by RABV-G-specific antibodies, on Days 1, 15, 43, and 12 months post last dose, on selected samples with VNT >0.5 IU/ml.

Additional exploratory testing, not defined in the objectives/endpoints, may be performed to further characterize the vaccine or immune response, including the development or improvement of tests related to the disease or the trial vaccines that will allow more reliable measurement of the response to the trial vaccines.

9.4 Trial Procedures

For each procedure, subjects are to be assessed by the same investigator or site personnel whenever possible. Refer to the Schedule of Activities (Table 2.1).

9.4.1 Visit 1 (Pre-screening Visit, Days -90 to -1)

Pre-screening visit activities can occur between 90 and 1 days prior to vaccination.

- Signed informed consent must be obtained prior to the subject entering into the trial, and before any protocol-directed procedures are performed.

The following procedures will be performed during the pre-screening visit:

- Collection of demographic information.
- Vital signs check (body temperature, pulse, blood pressure).
- Record medical history, including details of treatments for re-occurring conditions.
- Review of eligibility criteria. See sections 6.1 and 6.2
- Safety assessments (SAEs, intercurrent medical conditions, AEs leading to trial withdrawal, AESIs and MAAEs).
- Blood draw (section 9.5) for:
 - Thyroid-stimulating hormone (TSH), thyroid antibodies, antinuclear antibody (ANA) (~3 ml). Blood drawn at the pre-screening visit will be kept for retrospective measurement of TSH, thyroid antibodies and ANA following the occurrence of clinical autoimmune events (other autoantibodies might be investigated as well depending on the clinical autoimmune event).

